### **12.2. Adverse and Serious Adverse Events**

#### **12.2.1. Definition of Adverse Events**

##### **12.2.1.1. Adverse Event (AE)**

An AE is the development of an undesirable medical condition or the deterioration of a pre-existing medical condition following or during exposure to a pharmaceutical product, whether or not considered casually related to the product. In clinical studies, an AE can include an undesirable medical condition occurring at any time, including baseline or washout periods, even if no study treatment has been administered.

The investigator should, when certain, report a diagnosis rather than the signs, symptoms or clinically significant abnormal laboratory values associated with the AE. Otherwise, signs, symptoms or abnormal laboratory values may be used to describe the AE.

Any CS abnormality discovered prior to the first study medication treatment should be reported as medical history, not as an AE.

All AEs that occur from the time of first study medication application (V2) until 30 days after last study medication application must be documented in the subject's source documents and in the Aclaris' electronic data capture system.

#### **12.2.1.2. Serious Adverse Event (SAE)**

A serious adverse event is an AE occurring during any study phase (ie, baseline, treatment, washout, or follow-up), and at any dose of the investigational product, comparator or placebo, that fulfils one or more of the following:

- Results in death
- It is immediately life-threatening
- It requires in-patient hospitalization or prolongation of existing hospitalization
- It results in persistent or significant disability or incapacity
- Results in a congenital abnormality or birth defect
- It is an important medical event that may jeopardize the patient or may require medical intervention to prevent one of the outcomes listed above.

The term "life threatening" refers to an event in which the subject was at risk of death at the time of event; it does not refer to an event that hypothetically might have caused death if it were more severe.

Important medical events are those that may not be immediately life threatening, result in death or hospitalization, but are clearly of major clinical significance and may jeopardize the subject or require intervention to prevent one of the outcomes listed in the SAE definition above. These should also usually be considered serious.

SAEs will be reported from the time of informed consent until 30 days past last application of study medication, whether or not they are related to the study. SAEs will be documented on the Aclaris SAE report form and in the eCRF.

#### **12.2.1.3. Unexpected adverse event**

An AE is considered unexpected if it is not listed in the Investigator Brochure or is not listed at the specificity or severity that has been observed.

### **12.3. Recording Adverse Events**

#### **12.3.1. Adverse event reporting period**

The investigator must start reporting non-serious AEs with the subject's first study medication application and continue reporting until the end of the subject's last study visit. Reporting for SAEs must start when the subject signs the ICF and continue until the end of the subject's last visit.

### 12.3.2. Severity

The investigator is to define the severity of each AE using the following definitions as a guideline. The investigator will consider the range of the possible severity of the event and identify the severity that is the most appropriate according to her/his medical judgment.

**Mild** – Awareness of signs or symptom, but easily tolerated.

**Moderate** – Discomfort, enough to cause interference with usual activity.

**Severe** – Incapacitating with inability to perform usual activity.

### 12.3.3. Relationship to study medication

The investigator will determine if there is a reasonable causal relationship between the study medication and an AE or not. The investigator will use her/his best medical judgment and consider all relevant factors (*e.g.*, temporal relationship, location of the event, the subject's relevant medical history, concomitant therapies and concurrent conditions) to determine the relationship of the AE to the study medication. The investigator will define the relationship of an AE to the study medication by selecting one of the following categories:

**Related** – There is a reasonable causal relationship between the study medication and the AE.

**Not Related** – There is not a reasonable causal relationship between the study medication and the AE.

The expression “reasonable causal relationship” is meant to convey in general that there are facts (evidence) or arguments to suggest a causal relationship (International Conference on Harmonization [ICH] E2A).

### 12.3.4. Procedures for reporting adverse events

At each post-enrollment visit, the investigator will question the subject to elicit AEs using a non-directive question such as “Has there been any change in your health since the previous study visit?” If appropriate, based on the subject's response to non-directed questioning to elicit AEs, the investigator will follow-up with directed questions and appropriate evaluations.

Any AE noted during the reporting period must be reported in the source documents and on the appropriate AE eCRF. AEs that are defined as “Not Related” to the study medications will be followed until they are resolved or until the subject's last study visit. AEs that are defined as “Related” to the study medications will be followed until they are resolved or, if not resolved at the subject's last study visit, until in the opinion of the investigator, the AE reaches a clinically stable outcome with or without sequelae.

Should a pregnancy occur, it must be reported and recorded on Aclaris's pregnancy form. Pregnancy in itself is not regarded as an AE unless there is a suspicion that an investigational product may have interfered with the effectiveness of a contraceptive medication.

The outcome of all pregnancies (spontaneous miscarriage, elective termination, normal birth or congenital abnormality) must be followed up and documented even if the patient was discontinued from the study.

All reports of congenital abnormalities/birth defects are SAEs. Spontaneous miscarriages should also be reported and handled as SAEs. Elective abortions without complications should not be handled as AEs.

### **12.3.5. Procedure for reporting a serious adverse event**

Upon becoming aware of a SAE occurring during the SAE reporting period (time of subject consent until the end of the subject's last visit), whether or not related to the study medications, the investigator must:

1. Take the appropriate medical action to ensure the subject's safety.
2. Immediately inform the Safety Monitor of the SAE by email, ensuring that the subject information is deidentified (only subject initials and subject number) to: **ProPharma, Email: [contact].**
3. Print a copy of the email confirmation from ProPharma and place in the study file.
4. Within 24-hours complete, as fully as possible, an AE eCRF and an SAE form; e-mail the forms and any other relevant information (*e.g.*, concomitant medication eCRF, medical history eCRF, laboratory test results) to ProPharma (Aclaris Therapeutics, Inc. Safety Monitor).
5. Monitor and document the progress of the SAE until it resolves or, if not resolved after the subject's last study visit, until in the opinion of the investigator the AE reaches a clinically stable outcome with or without sequelae AND the investigator and Aclaris Therapeutics, Inc. Safety and Medical Monitor agree that the SAE is satisfactorily resolved.
6. Inform the Aclaris Therapeutics, Inc. Safety Monitor of SAE updates, via telephone, followed by an SAE form update sent by e-mail.

Comply with the appropriate regulatory requirements and Aclaris Therapeutics, Inc. instructions regarding reporting of the SAE to the responsible Institutional Review Board (IRB) or Ethics Committee (EC).

## **12.4. Pregnancy**

### **12.4.1. Definition of Women of Child Bearing Potential (WOCBP)**

WOCBP includes any female who has experienced menarche and who has not undergone successful surgical sterilization (*e.g.*, hysterectomy, bilateral tubal ligation, or bilateral oophorectomy) or is not postmenopausal. Postmenopausal is defined as  $\geq 12$  months with no menses without an alternative medical cause. WOCBP must have a negative serum pregnancy test at screening and a negative UPT at baseline prior to randomization.

### **12.4.2. Highly Effective Methods of Birth Control**

The Investigator or sub-investigator will discuss the potential risk factors associated with pregnancy and the importance of maintaining a highly effective method of contraception throughout the study with all WOCBP (for example, those which result in a low failure rate - *i.e.*, less than 1% per year- when used consistently and correctly). All WOCBP must use a highly

effective method of birth control during the study and for 30 days after the final application of study medication in a manner such that risk of failure is minimized.

Highly effective methods include:

- Combined (estrogen and progestogen containing) hormonal contraception associated with inhibition of ovulation:
  - oral
  - intravaginal
  - transdermal
- Progestogen-only hormonal contraception associated with inhibition of ovulation:
  - oral
  - injectable
  - implantable
- intrauterine device (IUD)
- intrauterine hormone-releasing system (IUS)
- vasectomized partner
- sexual abstinence

Vasectomized partner is a highly effective birth control method provided that partner is the sole sexual partner of the WOCBP trial participant and that the vasectomized partner has received medical assessment of the surgical success.

 Sexual abstinence is considered a highly effective method only if defined as refraining from heterosexual intercourse during the entire period of risk associated with the study treatments. The reliability of sexual abstinence needs to be evaluated in relation to the duration of the clinical trial and the preferred and usual lifestyle of the subject.

WOCBP must be on a highly effective method of birth control for the following timeframes prior to study entry:

- Implants (on a stable dose for  $\geq 90$  days)
- Injectables (on a stable dose for  $\geq 90$  days)
- Patches (on a stable dose for  $\geq 90$  days)
- Combined oral contraceptives (on a stable dose for  $\geq 90$  days)
- Intrauterine devices (inserted for  $\geq 30$  days).

Prior to trial enrollment, WOCBP must be advised of the importance of avoiding pregnancy during trial participation and of the potential risk factors associated with pregnancy while in the study. The subject must sign an informed consent form documenting this discussion. During the trial, all WOCBP will be instructed to contact the investigator immediately if they suspect they might be pregnant (*e.g.*, missed or late menstrual period).

If a subject or investigator suspects that the subject may be pregnant prior to study medication administration, the study medication must be withheld until the results of a pregnancy test are available. If pregnancy is confirmed, the subject must not receive study medication and must be discharged from the study.

If, following study medication administration, it is determined that the subject may have been or was pregnant at the time of study medication exposure (including at least 2 days after study medication administration) the investigator must immediately notify the Aclaris Therapeutics, Inc. Medical Monitor and record the event on a pregnancy surveillance form. While not an AE or SAE, the investigator must report every pregnancy using a pregnancy surveillance form and follow the reporting procedures described for SAE reporting.

Protocol-required procedures for trial discontinuation and follow-up must be performed on the subject unless contraindicated by pregnancy (*e.g.*, x-ray studies). Other appropriate pregnancy follow-up procedures should be considered if indicated. In addition, the investigator must report to Aclaris Therapeutics, Inc.'s Medical Monitor on the pregnancy surveillance form, follow-up information regarding the course of the pregnancy, including perinatal and neonatal outcome. Infants should be followed for a minimum of six weeks.

## **12.5. Protocol Deviation and Protocol Violations**

A *protocol deviation* is defined as an accidental or unintentional change to, or non-compliance with the research protocol that does not increase risk, or decrease benefit or; does not have a significant effect on the subject's right, safety, or welfare; and/or on the integrity of the data. Deviations may result from the action of the subject, researcher or research staff. A protocol deviation does not involve inclusion/exclusion criteria.

A *protocol violation* is defined as an accidental or unintentional change to, or non-compliance with the IRB approved protocol without prior sponsor approval. Protocol violations generally increase risk or decrease benefit, affects the subject's rights, safety, or welfare, or the integrity of the data.

## **13. STATISTICS**

### **13.1. Statistical Methods**

Summary descriptive statistics (N, mean, median, SD) by visit will be provided for all safety and efficacy parameters. The Intent to Treat population will be used for all efficacy assessments and the Safety population will be used for all safety assessments. No data imputation will be used. Primary and secondary efficacy parameters are described in the sections below.

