## **7.2. Number of Subjects**

A total of 24 evaluable subjects will be enrolled to the study (12 male and 12 female) at approximately 3 investigational centers.

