## 7.5. Schedule of Assessments

**Table 2: Schedule of Assessments-Initial 26 weeks of Treatment**

	Screening	Baseline	Treatment								Follow up Safety/Early Termination Visit 
	Visit 1	Visit 2	Visit 3	Visit 4	Visit 5	Visit 6	Visit 7	Visit 8	Visit 9	Visit 10	
			Week 3	Week 4	Week 8	Week 12	Week 16	Week 20	Week 24	Week 26	4 weeks post last application of ATI-50002
Treatment Day	-14 to 0	1	21	28	56	84	112	140	168	182	
Visit Windows	N/A	N/A	+/- 3 days	+/-4 days	+7 days	+/-7 days	+7 days	+/-7 days	+/-7 days	+7 days	+7 days
Informed Consent 	X										
Inclusion/Exclusion Criteria	X	X									
Demographics and Medical History	X										
Physical Exam 	X										X
Vital Signs 	X	X	X	X	X	X	X	X	X	X	X
Fitzpatrick Skin Type	X										
Prior Hair Treatment Assessment 	X										

	Screening	Baseline	Treatment								Follow up Safety/Early Termination Visit 
	Visit 1	Visit 2	Visit 3	Visit 4	Visit 5	Visit 6	Visit 7	Visit 8	Visit 9	Visit 10	
			Week 3	Week 4	Week 8	Week 12	Week 16	Week 20	Week 24	Week 26	4 weeks post last application of ATI-50002
Treatment Day	-14 to 0	1	21	28	56	84	112	140	168	182	
Visit Windows	N/A	N/A	+/- 3 days	+/-4 days	+7 days	+/-7 days	+7 days	+/-7 days	+/-7 days	+7 days	+7 days
Clinical Chemistry and CBC 	X				X		X		X	X	X
Quantiferon Gold 	X										
Total Iron Binding Capacity (TBIC), Serum Iron, Serum Ferritin	X										
Dihydrotestosterone (DHT), Testosterone, Estrogen, DHEA	X				X		X		X	X	X
Urine Pregnancy Test		X		X	X	X	X	X	X	X	X
Serum Pregnancy	X										
Serum PSA	X										
Thyroid Panel	X										
ECG	X			X						X	X

	Screening	Baseline	Treatment								Follow up Safety/Early Termination Visit 
	Visit 1	Visit 2	Visit 3	Visit 4	Visit 5	Visit 6	Visit 7	Visit 8	Visit 9	Visit 10	
			Week 3	Week 4	Week 8	Week 12	Week 16	Week 20	Week 24	Week 26	4 weeks post last application of ATI-50002
Treatment Day	-14 to 0	1	21	28	56	84	112	140	168	182	
Visit Windows	N/A	N/A	+/- 3 days	+/-4 days	+7 days	+/-7 days	+7 days	+/-7 days	+/-7 days	+7 days	+7 days
Norwood-Hamilton classification(males); Sinclair Scale (females)Assessment	X	X					X			X	X
Target Area Hair Identification and Tattoo application 		X									
Global Scalp Photograph 	X	X 			X 		X 			X 	X
Macro Scalp Photographs 		X			X		X			X	

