Target Area Hair Count (TAHC) and Target Area Hair Width (TAHW) 		X			X		X			X	
Demonstration of study drug application 		X		X	X	X	X	X	X	X 	
Dispensing of study medication 		X		X	X	X	X	X	X	X 	

	Screening	Baseline	Treatment								Follow up Safety/Early Termination Visit 
	Visit 1	Visit 2	Visit 3	Visit 4	Visit 5	Visit 6	Visit 7	Visit 8	Visit 9	Visit 10	
			Week 3	Week 4	Week 8	Week 12	Week 16	Week 20	Week 24	Week 26	4 weeks post last application of ATI-50002
Treatment Day	-14 to 0	1	21	28	56	84	112	140	168	182	
Visit Windows	N/A	N/A	+/- 3 days	+/-4 days	+7 days	+/-7 days	+7 days	+/-7 days	+/-7 days	+7 days	+7 days
Investigator Assessment of Hair Growth					X		X			X	
Subject Self - Assessment of Hair Growth					X		X			X	
Local Skin Reaction Assessment		X	X	X	X	X	X	X	X	X	X
Adverse Events 							X				
Concomitant Therapies							X				

A written, signed ICF must be obtained from each subject prior to performing any study related procedure

 A physical exam includes: general appearance, examination of head, eyes, ears, nose and throat, respiratory, cardiovascular, abdominal, neurological, musculoskeletal, lymphatic and skin assessment.

Vital signs include: oral or ear temperature, blood pressure, heart rate, respiration rate (height and weight at baseline only).

 Prior therapies or treatments a subject received to treat his/her AGA must be documented for each subject.

 Serum chemistry panel to include: albumin, alk phos, ALT, AST, BUN, bicarbonate, calcium, chloride, creatinine, glucose, lactate dehydrogenase (LDH), phosphorus, potassium, sodium, total bilirubin, total protein, uric acid, total cholesterol, LDL, HDL triglycerides, CPK, and complete blood count including differential.

 All subjects must have a blood sample drawn to test for the tuberculosis virus. The blood sample will be sent to a central laboratory for analysis and results must be received prior to enrolling the subject.

 The investigational study staff will be required to identify target area of the scalp that is located in an actively balding area. Directions for proper hair clipping are outlined in Section 9.2. Sites will be required to apply a permanent dot tattoo to the subject’s scalp to identify the target hair area.

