### **13.2. Primary Efficacy Endpoint**

Mean change from baseline in non-vellus TAHC will be quantified using a microphotographic technique and calculated along with the median, standard deviation, standard error, and 95% confidence limits around each mean change to allow tests of the null hypothesis that the population mean changes are zero.

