Appendix 16.2.3.9	Clinical Laboratory Assessments: Hematology
Appendix 16.2.3.10	Clinical Laboratory Assessments: Biochemistry
Appendix 16.2.3.11	Clinical Laboratory Assessments: Hormones
Appendix 16.2.3.12	Clinical Laboratory Assessments: Urinalysis
Appendix A	MedDRA System Organ Class/Preferred Term and CRF Verbatim Terms

MOCKUPS OF TABLES, AND PATIENT LISTINGS

Aclaris Therapeutics Inc.

23 Apr 2019 Statistical Analysis Plan

Protocol: ATI-50002-AGA-201

Table 14.1.1.1 Study Population and Patient Disposition

	Female n (%)	Male n (%)	Total n (%)
Population/Group			
Intent-to-Treat (ITT) Population	xx (100)	xx (100	xx (100
Safety Population	xx (100)	xx (100	xx (100
Entered 6 Month Extension	xx (xx.x)	xx (xx.x)	xx (xx.x)

Note: Percentages based on the number of patients receiving at least 1 treatment application

Table 14.1.1.2
Reasons for Discontinuation from Study
ITT Population

	Female (N=xxx) n (%)	Male (N=xxx) n (%)	Total (N=xxx) n (%)
ENTIRE STUDY ^a :			
Number (%) of Patients Discontinued	xx (xx.x)	xx (xx.x)	xx (xx.x)
Protocol Violation	xx (xx.x)	xx (xx.x)	xx (xx.x)
AE/SAE	xx(xx.x)	xx (xx.x)	xx (xx.x)
Lost to Follow-Up	xx(xx.x)	xx (xx.x)	xx (xx.x)
Withdrew Consent	xx(xx.x)	xx (xx.x)	xx (xx.x)
Pregnancy	xx (xx.x)	xx (xx.x)	xx (xx.x)
Other	xx(xx.x)	xx(xx.x)	xx (xx.x)
Completed 26 Week Study	xx(xx.x)	xx (xx.x)	xx (xx.x)
Completed Optional 6 Month Extension	xx(xx.x)	xx(xx.x)	xx (xx.x)
Ongoing as of "cut-off date"	xx (xx.x)	xx (xx.x)	xx (xx.x)
FIRST 26 WEEKS:			
Number (%) of Patients Discontinued	xx (xx.x)	xx (xx.x)	xx (xx.x)
Protocol Violation	xx(xx.x)	xx (xx.x)	xx (xx.x)
AE/SAE	xx(xx.x)	xx (xx.x)	xx (xx.x)
Lost to Follow-Up	xx(xx.x)	xx (xx.x)	xx (xx.x)
Withdrew Consent	xx (xx.x)	xx (xx.x)	xx (xx.x)
Pregnancy	xx(xx.x)	xx (xx.x)	xx (xx.x)
Other	xx(xx.x)	xx (xx.x)	xx (xx.x)
Completed	xx(xx.x)	xx(xx.x)	xx (xx.x)
Ongoing as of "cut-off date"	xx(xx.x)	xx (xx.x)	xx (xx.x)

^a Includes all discontinuations/completions from the first 26 weeks and optional 6 month extension. Patents completing both the initial 26 weeks and the 6 month extension periods are counted on both corresponding rows.

^b Used as denominator for percentages calculated under 6 month extension.

Table 14.1.1.2
Reasons for Discontinuation from Study
ITTSafety Population

	Female (N=xxx) n (%)	Male (N=xxx) n (%)	Total (N=xxx) n (%)
6 MONTH EXTENSION:			
Number of Patients Entering ^b	xx	XX	xx
Number (%) of Patients Discontinued	xx (xx.x)	xx (xx.x)	xx (xx.x)

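### The Week 26 and Week 52 hair-count means are observed-case estimates that leave out earlier leavers, although the efficacy population is labelled ITT

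*Protocol*

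**What the plan says.** - **Population and missing data.** Protocol 13.1: "The Intent to Treat population will be used for all efficacy assessments" and "No data imputation will be used". The note to SAP Table 14.1.1.1 reads "Percentages based on the number of patients receiving at least 1 treatment application", and the shell shows ITT as 100% on that base. Subjects who leave early therefore belong to ITT.
- **Primary analysis.** Protocol 13.2 reports the mean change in non-vellus TAHC with "95% confidence limits around each mean change to allow tests of the null hypothesis that the population mean changes are zero". It names no primary visit.
- **Table shell.** SAP Table 14.2.1.1 gives n, mean, SD, SE, median, range and CI for change, separately at V5, V7, V10 and V16. It has no early-termination row and no model. The shells for the global assessments and for AGA stage do have follow-up/early-termination rows.
- **Schedule.** In Protocol Table 2 the macro photograph row and the row "Target Area Hair Count (TAHC) and Target Area Hair Width (TAHW)" are marked at Visits 2, 5, 7 and 10 only. The follow-up/early-termination column is empty for both, while AGA stage and the global photograph are marked there. Table 3 adds Visit 16 only.
- **Size.** Protocol 7.2: "A total of 24 evaluable subjects will be enrolled to the study (12 male and 12 female"). No power, SD or drop-out figure is given.

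**The concern.** A subject who stops between Week 16 and Week 26 has counts at Weeks 8 and 16 but none at Week 26 and none at the termination visit. The Week 26 row then ignores that subject, although the earlier counts carry information about where the subject was heading. A subject who stops before Week 8 contributes no post-baseline count at all. The Week 52 row has the same weakness, and it also lacks those who did not consent to the extension.

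The trial is open-label, and from Week 8 subjects rate their own growth against baseline photographs. It is plausible, though not documented, that those who see little benefit leave more often. With no control arm, such selection would appear directly as a gain from baseline, and the comparison of the CI with zero would tend towards a false increase.

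**Working it through.** **Inputs.** From the documents: 24 subjects (Protocol 7.2), TAHC at baseline and Weeks 8, 16 and 26 (Table 2), and a two-sided 95% CI against zero (13.2). Not in the documents, so assumed: SD of change 15 hairs/cm², correlation 0.7 between visits, true mean change 0 at every visit, all drop-out after Week 16, and odds of leaving rising 1.5- to 3.3-fold per SD of poorer Week 16 change. The plan has no figure of its own to reproduce, since 24 is stated without a basis.

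**Step 1: simple formula.** Let d be the drop-out share and ρ the correlation between staying and the true change. Under normal selection,

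bias = ρ × φ(z_d) / (1 − d), in SD units.

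- d = 0.20, ρ = 0.5: φ(−0.842) = 0.280; 0.280/0.80 = 0.350; × 0.5 = 0.175 SD; × 15 = +2.6 hairs/cm².
- d = 0.10, ρ = 0.3: 0.195 × 0.3 = 0.058 SD; × 15 = +0.9.
- ρ = 0: bias 0 at any drop-out.

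**Step 2: simulation of the planned analysis** (8,000 to 20,000 trials per scenario; one-sample t interval on the subjects still present at Week 26).

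| Odds of leaving per SD of poorer Week 16 change | Drop-out | Mean Week 26 change (truth 0) | CI excludes zero (nominal 5%) |
|---|---|---|---|
| 1 (unrelated) | any | 0 | about 5% |
| 1.5 to 2 | 10–15% | +0.4 to +1.1 | 4.9–5.8% |
| 3.3 | 10% | +1.1 | 6.4% |
| 3.3 | 15% | +1.6 | 7.3% |
| 2 | 26% | +1.7 | about 8% |
| 3.3 | 26% | +2.6 | 11.1% |
| 3.3 | 33% | +3.3 | 14.2% |

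The excess is almost all on one side. At 26% drop-out and odds 3.3, a false increase occurs in 10.8% of trials against a nominal 2.5%. It falls to 6.7% with odds 2, and to 7.0% with odds 3.3 and correlation 0.5.

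**Step 3: scale.** The 95% CI half-width is 0.422 SD at n = 24, or 0.422 × 15 = 6.3 hairs/cm². At n = 18 (24 × 0.74 ≈ 18) it is 0.497 × 15 = 7.5. A bias of +2.6 at 26% drop-out is then about a third of the half-width (2.6/7.5 = 0.35).

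**Step 4: the alternative.** Regress the Week 26 change on the Week 8 and Week 16 changes in subjects with all three, then evaluate at the Week 8 and 16 means of all 24. This is the likelihood estimate for this drop-out pattern. When drop-out depends on the Week 16 change, its mean is 0.0 in the same scenarios, and an interval built on it excluded zero in 4–4.5% of trials.

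**Step 5: where the alternative falls short.** If leaving depends on the unobserved Week 26 change (odds 3.3), the observed-case mean is biased by +3.7 at 26% drop-out and +4.7 at 33%. The likelihood estimate is biased by +1.8 and +2.2, so about half the bias remains.

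**The case against.** A reader might infer that the plan is a completer analysis that throws away early leavers' data. It is not. Protocol 13.2 puts limits around each mean change, and SAP Table 14.2.1.1 uses every count at Weeks 8 and 16, each row with its own n. The analysis is observed-case by visit. Week 26 is only a natural reading of the main time point, as the end of the first treatment period.

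A reader might also infer that the CI against zero is invalid. That would need drop-out linked to response, which the documents neither state nor quantify. Subjects judge global photographs, whereas TAHC is measured by blinded technicians, and nothing says subjects learn their counts. How closely perceived growth follows TAHC is itself a planned output (SAP Table 14.2.6). A 3.3-fold odds ratio tied directly to TAHC is therefore a strong assumption, and under mild selection the error rate hardly moves.

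Other points also stand:
- The termination visit falls 4 weeks after the last application, so omitting a count there is defensible.
- The SAP already tabulates discontinuations by reason and period and lists individual counts.
- The no-imputation rule does not bar a likelihood model, which imputes nothing.
- The SAP available here is mainly table and listing shells, so a missing-data statement in its text part cannot be ruled out.
- The estimator checked in Step 4 has no sex terms and stands in for the fuller model proposed.

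These points limit the size and certainty of the concern. They do not remove it: the Week 26 row omits earlier leavers, and the shells show no estimate that uses their earlier counts.

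**Conclusion.** The concern holds as a conditional one. The Week 26 and Week 52 TAHC rows are observed-case estimates that leave out earlier leavers, under an ITT label that includes them.

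Under the stated assumptions the upward bias at Week 26 is about +0.4 to +1.6 hairs/cm² at 10–15% drop-out (odds 1.5 to 3.3; CI excludes zero in about 5–7% of trials). It is +1.7 to +3.3 at 26–33% drop-out (odds 2 to 3.3; about 8–14%). Weaker selection gives less, and drop-out unrelated to response gives none. SD, correlation, drop-out rate and strength of selection are all assumptions.

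It would also be too strong to say that a likelihood model makes the estimate unbiased. It does so only when drop-out depends on counts already observed.

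**What to change.** Add to the SAP a repeated-measures likelihood model of TAHC change at V5, V7 and V10, with visit, sex, visit × sex, unstructured covariance and small-sample degrees of freedom. Include every subject with at least one post-baseline count. Take the Week 26 mean and 95% CI from the model. Keep Table 14.2.1.1 as support, labelled observed-case, including its Week 52 row.

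State the limits beside it: the model removes bias only when drop-out depends on observed counts, reduces but does not remove it otherwise, and cannot include subjects who leave before Week 8.

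Optionally, mark the macro photograph and TAHC in the early-termination column of Tables 2 and 3. If taken at the scheduled visit, the value must be labelled as about 4 weeks off drug.

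Cost: one extra model on counts already collected. The optional count adds one clipping and photograph per early leaver, with equipment already on site, and a protocol amendment.
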